Title: Role of Platelet Rich Plasma in supporting the recovery of post-partum Levator Ani Muscle trauma

Running title: Platelet rich plasma in levator ani muscle trauma

NCT number: **NCT03021954**

Document date: January 15th, 2018

Financial dislaimer: None

STUDY PROTOCOL

Participant Flow

We obtained 245 primigravid women. As many as 85 subjects underwent caesarean section because of clinical indications, 39 subjects were failed to follow the study until the end and 5 subjects were found to have avulsion after 40 days post-partum. Overall, there were 58 subjects who successfully followed the examination until the end of the study.

Study Procedure

- a. All patients who come to Polyclinic in Public Health Center (Puskesmas) will be taken a history and physical examination to determine whether the patient meets the criteria or not,
- b. Patients who met the criteria were provided with information about this study. Patients who are willing will be asked to fill out an informed consent. If the patient refuses to participate in this study, the reasons for refusal must be written,
- c. Randomization was performed and participant were divided into 2 groups (intervention group and control group). Participant will not know the results of randomization. Participant may know the results of randomization at the end of the study,
- d. Initial data collection on study form and approval to participate will be taken. Participants are required to write down their full name, complete address, phone number, and family phone number. This is an attempt to increase the participation rate.
- e. Participant will be examined by ultrasound to assess pelvic floor biometry, perineometry to assess pelvic floor muscle strength,
- f. At delivery day, the participant in intervention group will be taken whole blood for preparation of 32 mL of PRP. After the PRP is ready, it will be injected directly into the levator ani muscle during post-partum perineorrhaphy,
- g. Participant in control group will still have whole blood taken for examination (complete blood count) but no PRP preparation will be carried out. During perrineorrharphy will be injected lidocaine 1%. In this way, it is hoped that the participant will now know that she is in the intervention or control group,

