Title: Role of Platelet Rich Plasma in supporting the recovery of post-partum Levator Ani Muscle trauma

Running title: Platelet rich plasma in levator ani muscle trauma

NCT number: NCT03021954

Document date: January 15th, 2018

Financial dislaimer: None

Study Analysis Plan (SAP)

• Estimated Sample Size

$$n1 = n2 = 2\left(\frac{(Z\alpha + Z\beta)S}{X1 - X2}\right)^2$$

Information:

n = Number of samples

 α = type I error is set at 5 %, the hypothesis is in the direction of $Z\alpha$ = 1.64

 β = type II error is set at 10 %, the hypothesis is in the direction of Z β = 1,28

X1 - X2 = the minimum difference that is considered significant

- Measurement of the levator hiatal area during valsalva, the researchers set a value of X1-X2 = 5. From the journal about the levator ani hiatus area during Valsalva, it was obtained SD = 6.09. The sample size for each group was 23 subjects.
- Measurement of the strength of the levator ani muscle contraction, the researchers set a value of X1-X2 = 9. From the journal on the strength of the levator ani muscle contraction, it was obtained that SD = 11.63. The sample size for each group was 27 subjects.
- The drop out number of samples is added by 20%. Thus, the total sample is 65 people.

Sampling Method

The sample was taken consecutively. The researcher took subjects who met the inclusion criteria and passed the exclusion criteria until the target number of subjects was met. Randomization using online randomizer. Subjects were divided into two groups, namely the intervention group with PRP injection and the control group.

Daya Analysis

Data were analyzed using Statistical Product and Service Solutions version 20 (SPSS version 20). Univariate analysis was performed for each variable and then presented in terms of frequency and percentage. For the bivariate analysis of the intervention and control groups with certain independent variables used unpaired categorical comparative

analysis of 2 groups using the Mann-Whitney test, paired comparative analysis of 2 groups using the Willcoxon test. If p < 0.25, then multivariate analysis was performed.

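### The SAP makes adjustment depend on an unidentified p < 0.25, does not fix the deciding analysis or visit, and does not say the arm comparison uses the baseline measurements

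*SAP*

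**What the plan says.** The SAP's data analysis section (headed Daya Analysis) describes the bivariate step as a comparison of the "intervention and control groups with certain independent variables used unpaired categorical comparative" variables, continuing with "analysis of 2 groups using the Mann-Whitney test" for unpaired data and the Wilcoxon test for paired data. It closes with "If p < 0.25, then multivariate analysis was performed". That is the whole inferential plan. The section names neither hiatal area nor contraction strength, and it does not say whether follow-up values or changes are compared.

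The sample size section does name two outcomes: "Measurement of the levator hiatal area during valsalva, the researchers set a value of X1-X2 = 5" and "Measurement of the strength of the levator ani muscle contraction, the researchers set a value of X1-X2 = 9". It works one-sided: "type I error is set at 5 %, the hypothesis is in the direction of" Z = 1.64.

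The protocol's Study Procedure, step e, reads: "Participant will be examined by ultrasound to assess pelvic floor biometry, perineometry to assess pelvic floor muscle strength". Step f is the delivery-day step, so the step-e values are inferred to be antenatal, although step e carries no date. Step h repeats both measures at 40 days and at 3 months. Participant Flow already reports "58 subjects who successfully followed the examination until the end of the study".

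**The concern.** The p in the rule can be read in at least three ways: the p of the treatment comparison, the p of a covariate screened against the outcome, or the p of a baseline difference between arms. Each leads to a different procedure. Under all three, the data determine whether the arm comparison is adjusted, and the SAP does not say which result carries the conclusion if the rank test and the model differ. With two visits and no primary visit, the quantity being tested is open as well.

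The step-e values are the natural covariates, yet nothing says the arm comparison uses them. The paired Wilcoxon test could use them, but only for change within an arm, which does not compare the arms. At stake are clarity about what decides the trial, some power and precision and, if the choice between results stays open, a modest excess of false positives.

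**Working it through.** **1. Design inputs (SAP, sample size).** Strength: difference 9, SD 11.63, so d = 9/11.63 = 0.774. Area: difference 5, SD 6.09, so d = 5/6.09 = 0.821. Z values are 1.64 and 1.28.

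**2. The plan's own figures.** For strength, 2 × ((1.64 + 1.28) × 11.63/9)² = 28.5, or 29 per group; the SAP states 27. For area the same formula gives 25.3, or 26; the SAP states 23. The total follows from 27: 2 × 27 × 1.2 = 64.8, or 65. The stated 27 per arm is used below; the small differences do not bear on this point.

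**3. What baseline adjustment can do.** With correlation ρ between baseline and follow-up, adjustment multiplies the SD by √(1 − ρ²). By the normal approximation, unadjusted power is Φ(9/(11.63 × √(2/27)) − 1.645) = Φ(2.843 − 1.645) = 0.885. Dividing 2.843 by √(1 − ρ²) gives 0.909, 0.949 and 0.990 at ρ = 0.3, 0.5 and 0.7. The documents give no ρ, so a range is shown throughout.

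**4. Power under each reading.** Simulation: bivariate normal data, strength, 27 per arm, one-sided 5%. There were 200,000 replicates for strength and the null and 40,000 elsewhere, so the Monte Carlo error is at most 0.25 points. Where a screen leaves baseline out, Mann-Whitney on follow-up is used. The treatment trigger is a two-sided Mann-Whitney p < 0.25.

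| Deciding analysis | ρ 0.1 | 0.3 | 0.5 | 0.7 | Loss against fixed ANCOVA, points |
|---|---|---|---|---|---|
| Fixed ANCOVA | 0.875 | 0.896 | 0.941 | 0.988 | – |
| Covariate screened on outcome | 0.866 | 0.892 | 0.941 | 0.988 | 0.9 / 0.4 / 0.0 / 0.0 |
| Model triggered by treatment p | 0.874 | 0.890 | 0.920 | 0.942 | 0.1 / 0.6 / 2.1 / 4.6 |
| Covariate screened on baseline difference | 0.865 | 0.873 | 0.894 | 0.921 | 1.0 / 2.3 / 4.7 / 6.7 |
| Mann-Whitney, follow-up | 0.863 | 0.862 | 0.863 | 0.862 | 1.2 / 3.4 / 7.8 / 12.6 |
| Mann-Whitney, change | 0.655 | 0.747 | 0.865 | 0.971 | 22.0 / 14.9 / 7.6 / 1.7 |

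A plain t-test has power 0.878, so about 1.5 points of the gap to Mann-Whitney (0.878 − 0.863) is t-test over rank test on normal data. At ρ = 0.1 that accounts for all of it. The baseline-difference screen does badly because randomised arms differ only by chance: baseline enters in about 25% of trials however prognostic it is.

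With 29 per arm (58 completers, equal split assumed) the pattern is the same: Mann-Whitney 0.88, ANCOVA 0.895/0.916/0.954/0.991. For area at 27 per arm: Mann-Whitney 0.894–0.897, ANCOVA 0.907/0.924/0.960/0.993.

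**5. Type I error (two-sided 5%, same ρ values).**

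| Rule | Error, % |
|---|---|
| Mann-Whitney on follow-up | 5.0 |
| Fixed ANCOVA | 4.9–5.0 |
| Outcome screen | 5.0 / 5.0 / 4.9 / 5.0 |
| Treatment trigger, model reported | 4.9 / 4.9 / 4.4 / 3.6 |
| Baseline-difference screen | 5.0 / 4.6 / 3.8 / 2.7 |
| Either Mann-Whitney or triggered model may be claimed | 6.2 / 6.6 / 6.9 / 7.0 |

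On the SAP's one-sided scale the last row is 6.0 / 6.2 / 6.3 / 6.4.

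**6. Skewed data (lognormal, strength, one-sided, ρ = 0.1).** At log-SD 0.3, Mann-Whitney has about 0.90–0.91 and linear ANCOVA 0.876, a loss of about 3 points. At log-SD 0.5 the figures are 0.95–0.96 and 0.872, a loss of about 8 points. Linear ANCOVA draws level only at ρ of about 0.35–0.4 and 0.6 respectively. Rank ANCOVA (Quade) gives 0.902 and 0.952 at ρ = 0.1, and is 1–2 points below linear ANCOVA on normal data.

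**The case against.** A cut-off of 0.25 may be meant only as a screen of covariates against the outcome. Under that reading the loss is at most 1 point with no inflation. This stands as to size, but the SAP does not say so, and even then it does not name the deciding result.

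Mann-Whitney is valid, the SAP names only rank tests, and deleting the rule while naming Mann-Whitney on one quantity at one visit would already cure the ambiguity. This stands too. Baseline adjustment is a gain in efficiency, not a repair of validity. The gain depends on an unknown correlation, with delivery lying between the two measurements, and linear ANCOVA can lose on skewed data.

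Two stronger readings are tempting. A reader might infer that the p < 0.25 rule itself inflates type I error. It does not: every fixed reading checked is at or below 5%, and the excess needs a freedom to claim either result, which the SAP leaves open but does not state. A reader might also count as a separate harm that Mann-Whitney and ANCOVA give different verdicts in about 5 to 13% of trials. Most of that is already priced. At zero correlation they still differ in 4.4% of trials, mainly rank test against t-test, and at 0.7 almost all the differences are trials that only ANCOVA wins, which is the power gap again.

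**Conclusion.** The point holds as a gap in specification together with a cheap missed improvement. The trigger, the model, the visit and the deciding result are not fixed, and no use of the step-e values in the arm comparison is stated. The size depends on the reading: from almost nothing under an outcome screen to 13 points of power if Mann-Whitney on follow-up decides and the correlation is high. Change scores analysed by Mann-Whitney would be far worse at low correlation. These figures assume normal data, one baseline covariate, equal arms and correlations that the documents do not supply.

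The documents do not support saying that the planned test is invalid or that the error rate is necessarily inflated. Nor do they show whether outcomes had been seen when the rule was written: the past tense and the reported completers raise the question without answering it. The plan should be corrected, but the defect does not by itself invalidate the trial.

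**What to change.** - Delete the p < 0.25 rule.
- For each outcome, name one deciding arm comparison at one visit chosen by the sponsor: the follow-up value on arm plus the same measure's step-e value, reported as an adjusted difference with a 95% CI.
- If marked skew is expected, use rank ANCOVA (Quade) for the test, and choose between the two from the baseline values alone.
- Adjust hiatal area only if the step-e value was measured under the same condition as follow-up. The sample size refers to area during Valsalva, but SOP 2 mentions that manoeuvre only at step 6, for the levator urethral gap, after area is traced at step 5.
- Keep Mann-Whitney on the follow-up value as a sensitivity analysis.
- If outcomes had already been seen, drop the rule, keep Mann-Whitney on follow-up as the planned test, and label the adjusted analysis post hoc.

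The cost is SAP wording, one degree of freedom per model and a check of how step-e area was measured; no new data are needed. Near a correlation of 0.1 the gain is about 1 point or less. How the two outcomes rank against each other needs its own rule.
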